**7.1.1.3. Population of Interest**

PP population.

**7.1.1.4. Strategy for Intercurrent (Post-Randomization) Events**

For the primary efficacy analysis, the intercurrent event of interest is occurrence of a protocol deviation considered to impact efficacy during the treatment period (see [Appendix 1](#)). An ‘as treated’ strategy will be used to account for this event - only Month 6 E-RS: COPD data (see Section [14.6.3](#)) collected prior to the occurrence of a protocol deviation considered to impact efficacy will be used in the analysis.

The intercurrent event of treatment discontinuation is accounted for in the endpoint definition as only data at Month 6 will be used.

**7.1.1.5. Statistical Analyses / Methods**

**7.1.1.5.1. Statistical Methodology Specification**

Endpoint / Variables

 
Change from baseline in Month 6 E-RS: COPD total score
 

Model Specification

Bayesian dose response model:
 
 
Models of the following form will be considered:  <math>Response = E_0 + E_{max} * f(dose)</math> 
 
Log-linear model: <math>f(dose) = \log(dose + 0.01)</math>, where 0.01 is an offset to allow the model to fit for zero dose (placebo).
 
3-parameter emax model: <math>f(dose) = dose / (dose + ED50)</math>
 
4-parameter emax model: <math>f(dose) = dose^m / (dose^m + ED50^m)</math>
 
 
 
 
Where:
 
 
<math>E_0</math> = the response at dose = 0 (placebo),
 
<math>E_{max}</math> = the maximal response over placebo,
 
<math>ED50</math> = the dose that yields 50% of the maximal response,
 
<math>m</math> = dose-response slope parameter.
 
 
 
The log-linear, 3-parameter emax and 4-parameter emax model will be fitted without adjusting for covariates. If possible, covariates (i.e., baseline, smoking status, country) will be included in the <math>E_0</math> and <math>E_{max}</math> terms of the model for the final analysis
 
Normal non-informative priors will be used for the <math>E_0</math> and <math>E_{max}</math> parameters with mean 0 and SD 100. A FUP will be used for the <math>ED50</math> and <math>m</math> parameters (Bornkamp, 2014), where the
 

prior density for the FUP is based on all the parameters in the model. An inverse -gamma prior with shape of 0.001 and scale of 0.001 will be used for the residual variance.

- Parameters will be blocked such that the MCMC procedure samples from E0 and Emax first, then the ED50 and m parameters and then finally the residual variance parameter.
- For the functional uniform priors, the density will be calculated for values of dose from 0.0001 to 50 in steps of 5 (i.e. 0.0001, 5.0001, 10.0001, ..., 50.0001).
- 3 MCMC chains will be fitted using the following starting values (as required for the parameters in each particular model):

Parameter	Chain 1	Chain 2	Chain 3
E0	Posterior mean for placebo from MMRM at Month 6 (See Section 7.1.3)	-15	15
Emax	Posterior mean for 50mg dose from MMRM at Month 6 (See Section 7.1.3)	15	-15
ED50	25	10	50
M	1	2	4
Residual variance	6	8	10

- 100,000 MCMC samples will be generated using a thin of 50 to leave 2000 retained samples, and after a burn-in of 10,000 samples for each of the three sets of starting values. All post-burn-in samples from the 3 chains will be used for inference. The number of samples generated and the thin may be increased to reduce the ratio of the MCSE to the posterior SD, as deemed necessary.
- The seeds used to for the three chains were generated using the ranuni function in SAS and are listed in Section 14.5.2.
- The best fitting model will be the model with the smallest average DIC over the 3 chains where convergence is deemed to have been achieved. If the best fitting model is one that adjusts for covariates, all outputs will be presented adjusting for the mean in the observed covariate.
- Production and QC will be deemed to have agreement if the QC value is the following range:
  - if a number is reported to 0dp and there is a difference of  $\pm 1$  (number of participants must agree)
  - if a number is reported to 1dp and there is a difference of  $\pm 0.1$
  - if a number is reported to 2dp and there is a difference of  $\pm 0.01$
  - if a number is reported to 3dp and there is a difference of  $\pm 0.001$
  - if a number is reported to 4dp and there is a difference of  $\pm 0.0001$

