10.2. Sample Size Determination

[figure not shown]
In order to evaluate the impact of different sample sizes, various simulations were undertaken to understand the following questions around the change in baseline of E-RS:COPD scores at 6 months:

- What is the 90% confidence interval half width for the estimate of the treatment effect of the 5 mg, 25 mg, 35 mg, and 50 mg doses?
- What is the probability that the point estimate of difference from placebo is less than -1.5 for the 5 mg, 25mg, 35mg and 50 mg doses?
- What is the probability that the two-sided 90% confidence interval of the treatment effect excludes 0 for 5 mg, 25 mg, 35 mg and 50 mg doses?
- What is the probability that the two-sided 90% confidence interval of the treatment effect difference from placebo excludes 0 for 5 mg, 25 mg, 35 mg and 50 mg doses?

There are 3 scenarios considered for the simulations, each based on different assumptions of the effect for each of the 6 treatment arms. No model assumptions were made to generate these values. The scenarios are found in [Table 4](#) and [Figure 2](#). The assumed between participant standard deviation is 6.5 which is based on interim data from the 200163 study. For each scenario, 10,000 iterations of simulations were run.

Table 4 Assumptions Used for Sample Size Calculations

	Scenario 1	Scenario 2	Scenario 3
Placebo	0	0	0
5 mg	-0.5	-0.333	-0.5
10 mg	-1	-0.667	-0.75
25 mg	-2	-1.333	-2
35 mg	-2.5	-1.667	-2
50 mg	-3	-2	-2

Figure 2 Simulation scenarios with best fit sigmoidal Emax model

The Emax model will be used for the primary analysis and was the basis for estimation of the simulated data. The more general 4 parameter version of this model is defined as:

$$y(\text{dose}) = E_0 + E_{\text{max}} \left[\frac{\text{dose}^m}{(ED_{50}^m + \text{dose}^m)} \right]$$

where $y()$ represents the E-RS:COPD change from baseline, E_0 is the mean response at dose = 0, E_{max} is the maximum dose effect (at dose = ∞), ED_{50} is the dose that yields a mean response of $E_0 + E_{\text{max}} / 2$, and m is the slope parameter allowing for sigmoidal dose response relationships.

Results of the sample size simulations are presented in [Figure 3](#), [Figure 4](#), [Figure 5](#) and [Figure 6](#), with the lowest danirixin dose (5 mg) and the 3 highest doses (25 mg, 35 mg, 50 mg).

Figure 3 Half width of the 90% confidence interval for the 5 mg, 25 mg, 35 mg and 50 mg doses

[figure not shown]

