10.5.1. Efficacy Analyses

10.5.1.1. Primary Analysis

The primary endpoint is 6 month change from baseline using the mITT population.

Baseline values of E-RS: COPD will be defined as the daily average of scores for the 7 days prior to randomization. Days with missing values will not count towards the average. A minimum of 4 days will be needed and participants without sufficient days will not be randomized.

Individual monthly E-RS:COPD means will be defined as the average E-RS:COPD scores during the following study days:

- Month 1: days 1-28
- Month 2: days 29-56
- Month 3: days 57-84
- Month 4: days 85-112
- Month 5: days 113-140
- Month 6: days 141-168

Days with missing values will not factor into the calculations. Participants will require a minimum number of 10 observations within a month, otherwise the monthly mean will be considered missing for that patient.

The primary analysis will be Emax (4 parameter) modeling of the dose-response curve for the primary efficacy endpoint of month 6 change from baseline. Smoking status will be included as a covariate in this model, allowing the asymptote values of the dose-response relation for smokers to differ from those of the non-smokers. This model formulation will require estimation of at most six parameters. Simpler models nested within this general formulation will be also considered, comprising formulations of the mean dose-response relation allowing for a fixed difference between smokers and non-smokers (parallel curves model), no difference between smokers and non-smokers and the Emax model restriction $m=1$. Model fitness will be measured using standard goodness of fit analysis. This analysis will allow for an assessment of the extent to which the variability of the trial data will be captured using the proposed model and what dose-response specification allows the best interpretation of the data.

The dose-response model will be fitted to the data using Bayesian techniques using the function uniform prior (FUP). The rationale for this choice of inference is that the FUP shrinks the dose-response towards a flat line throughout the dose range, therefore providing more conservative estimates of the dose-response relation compared to maximum likelihood.

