Standard Bayesian diagnostic plots will be produced to aid in the interpretation of results. Based on the selected model, 90% two sided Bayesian credible interval for all treatment arms, all pairwise differences between each danirixin dose and placebo, as well as between active danirixin doses, will be generated.

Other models of dose response such as quadratic and log linear will be considered as alternative analysis option if the Emax model does not fit the data well. Similar analysis with the final model using the endpoint includes months 1-6 and months 3-6 will be fit. A longitudinal mixed effects model will be also be fit with dose as a categorical variable to explore the time trend of E-RS:COPD. Each of the three E-RS:COPD subscales (breathlessness, cough and sputum, and chest symptoms) will be analysed using similar methods for the primary analysis and longitudinal analysis. Details of these sensitivity analyses will be further described in the RAP.

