**Model Results Presentation**

The following will be presented for each analysis based on the best fitting model using all post-burn in samples available.

- The posterior mean, median, SD and 90% credible interval (CrI) for the change from baseline in E-RS: COPD total score for each treatment group.
- The posterior mean and 90% CrI for the difference from placebo for each danirixin dose.

- The posterior probability that difference from placebo is less than 0, -0.5, -1, -1.5 and -2 for each danirixin dose.
- For the strategic interim, the posterior predictive probability of success for each danirixin dose, where success is the probability that the difference from placebo is less than 0 is >95%.
- A figure of the fitted mean dose response model with the 90% CrI for all possible doses in the dose range, overlaid with the Month 6 adjusted posterior means and 90% CrI from the longitudinal model in Section 7.1.3.

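### The SAP lets log(dose + 0.01) compete on equal terms for the primary dose-response result, although the protocol admits log-linear only if Emax fits poorly; SAP Table 1 does not record the change

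*SAP*

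**What the plan says.** Protocol 10.5.1.1 sets an order. First: "The primary analysis will be Emax (4 parameter) modeling of the dose-response curve". Next to it: "Simpler models nested within this general formulation will be also considered", and the examples given are smoking-effect variants and the restriction m = 1. Last come other shapes: "quadratic and log linear will be considered as alternative analysis option if the Emax model does not fit the data well". Protocol 10.2 rests the sample size on the same family: "The Emax model will be used for the primary analysis and was the basis for estimation of the simulated data".

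SAP 7.1.1.5.1 has no such order. It lists log-linear, 3-parameter Emax and 4-parameter Emax as candidates and fits all three. The log-linear form uses log(dose + 0.01), "where 0.01 is an offset to allow the model to fit for zero dose (placebo"). Selection is by one rule, subject to convergence: "The best fitting model will be the model with the smallest average DIC over the 3 chains". The dose-level posterior summaries "will be presented for each analysis based on the best fitting model using all post-burn in samples available".

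SAP 2.1 says that Table 1 sets out changes from the protocol analysis. The table goes down to a move from 95% to 90% intervals but has no row on the candidate models. Its one dose-response row concerns the months analysed and still speaks of a final Emax model. The RAP amendment log in SAP 1.1 is also silent.

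**The concern.** DIC is a relative measure that penalises complexity. A two-parameter mean curve can beat a four-parameter one while Emax fits adequately, and that is not the condition the protocol sets for using log-linear.

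The log-linear form has no free shape parameter. The offset has no stated pharmacological basis, yet it sets how much of the 50 mg effect is credited to the low doses. Both documents defend the functional uniform prior as shrinking towards a flat curve and so being conservative. That prior acts on ED50 and m, which log-linear does not have. At stake is the low end of the curve, in a study that protocol 5.4 says should help select the minimal effective dose.

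**Working it through.** **1. The plan's own figure.** Inputs from the protocol: SD 6.5 and 35 mg effects of -2.5, -1.667 and -2 (10.2, Table 4); 600 participants allocated equally, so 100 per arm; 90% two-sided intervals (10.5). A pairwise comparison has SE = 6.5 × √(2/100) = 0.919, and its interval excludes 0 in 86%, 57% and 70% of trials (scenarios 1, 2, 3). That does not reach the stated figure of over 80% in all scenarios. Simulated Emax fits do (1,200 trials; assumed ED50 0.5-75, m 0.5-6, SD known): 99.3%, 84.8%, 89.7% with three parameters and 99.6%, 85.9%, 89.5% with four. Log-linear used alone gives 95.3%, 69.6%, 79.8%. The planning statement therefore rests on Emax.

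**2. Shape fixed by the offset.** The effect over placebo at dose d is slope × [ln(d + 0.01) - ln(0.01)] = slope × ln(100d + 1). As a share of the 50 mg effect this is ln(100d + 1)/ln(5001):

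| Dose | Log-linear share | Table 4 share (scenarios 1, 2, 3) | Exposure-based share |
|---|---|---|---|
| 5 mg | ln 501/ln 5001 = 73% | 17%, 17%, 25% | 48% |
| 10 mg | ln 1001/ln 5001 = 81% | 33%, 33%, 38% | 67% |
| 25 mg | ln 2501/ln 5001 = 92% | 67%, 67%, 100% | 89% |
| 35 mg | ln 3501/ln 5001 = 96% | 83%, 83%, 100% | 95% |

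The last column uses Cavg/(Cavg + 78.5) from protocol Table 2 with Hill coefficient 1 assumed. At 5 mg: 57.2/135.7 = 0.4215; at 50 mg: 571/649.5 = 0.8791; ratio 0.48. The 5 mg log-linear share depends on the offset: 82.5% at 0.0001, 63.2% at 0.1, 45.6% at 1.

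**3. Consequence if log-linear is the reported model.** Least-squares fits of log-linear to the true Table 4 means give 5 mg effects of -1.86, -1.24 and -1.45 (truth -0.5, -0.333, -0.5). At 35 mg they give -2.44, -1.63 and -1.90 (truth -2.5, -1.667, -2).

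**4. How often it is selected, and what that costs.** Simulated contests used 90 per arm (10% dropout), SD 6.5, the functional uniform prior and no covariates. The SAP does not settle three inputs, so each was varied: the ED50 and m bounds; whether the prior carries an Emax factor; and whether DIC is evaluated at posterior parameter means or at posterior fitted means. Separate runs disagree for the parameter-mean version, so both are shown.

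| DIC version, Table 4 scenarios | Log-linear selected | Change in 5 mg 90% coverage if log-linear is dropped |
|---|---|---|
| Parameter means, 500 trials per setting | 0-5% | -0.4 to +1.0 points |
| Parameter means, 2,000 trials per setting | 0-16% | -0.2 to +7.6 points |
| Fitted means, across runs | about 10-30% | about +3 to +15 points |

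With a flat response, log-linear was selected in about 20% (parameter means) to 46% (fitted means) of trials at 100 per arm. In the 2,000-trial runs, dropping it moved 35 and 50 mg coverage by -0.4 to +2.6 points under either DIC.

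**The case against.** The strongest reply is that this is mostly a wording gap. The protocol itself names log-linear, plans goodness-of-fit work to settle the specification, gives no threshold for poor Emax fit, and leaves detail to the RAP. DIC is a criterion fixed in advance. All of that is true. It explains why a fit statistic appears, but it does not remove the stated condition that Emax must first fail.

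The second reply is that the effect may be nil. SAP 7.1.1.5.1 says that the "prior density for the FUP is based on all the parameters in the model". The closest reading is a prior with the Emax factor. Combined with parameter-mean DIC, that gave selection in 0.1-3.6% of Table 4 trials and at most 0.2 points of 5 mg coverage. The larger losses mostly need fitted-mean DIC, which neither document mentions. This stands, and it limits the severity. The simulations also omit the covariates that the SAP would include if possible.

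Third, there are safeguards. The categorical-dose Bayesian MMRM reports Month 6 differences and the same threshold probabilities, and its means are overlaid on the fitted curve. These would help reveal a misfit at 5 mg, but the primary summaries would still come from the selected model.

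Two stronger readings do not hold. A reader might infer that the sample-size statement fails. It fails only if log-linear is always used: with the three-way contest under fitted-mean DIC and 100 per arm, the 35 mg figure stayed at 99.8%, 87.4% and 91.3%. A reader might also infer that an Emax-only contest is better whatever the true curve. If the truth is log-linear, runs ranged from about 4 points better to 9 points worse for 5 mg coverage. For the exposure-based curve with parameter-mean DIC they ranged from -5.4 to +7.3.

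**Conclusion.** The departure is established from the text: log-linear is conditional in the protocol, unconditional in the SAP, and absent from SAP Table 1. The 73% and 81% shares are exact and hold whenever log-linear is selected. They would overstate the 5 and 10 mg effects under every Table 4 scenario, and by less against the exposure-based shape.

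How often this would happen is uncertain. It depends on the DIC definition, the bounds and the form of the prior, and all the selection rates and coverage changes above rest on assumed values for these. Under the planning scenarios the loss in 5 mg coverage runs from nothing to roughly 15 points, with the low end more likely on the closest reading of the SAP. Results at 35 and 50 mg are essentially unaffected. Severity is minor to moderate.

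**What to change.** In SAP 7.1.1.5.1, restrict the DIC selection to 4-parameter Emax and its nested 3-parameter form. Report log-linear as a sensitivity analysis, or allow it as the primary model only when Emax fails a lack-of-fit criterion stated in advance. List any remaining departure in SAP Table 1 with a reason; the protocol's quadratic option has also been dropped without a row.

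Small edits to make at the same time: state where DIC is evaluated and the bounds on ED50 and m, and correct the parameter definitions for the log-linear form. There, E0 is the response at 0.99 mg, because log(0.99 + 0.01) = 0, and Emax is a slope with no maximum.

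The cost is wording only; no new model or data are needed. Under Table 4 the mean width of the 5 mg 90% interval changes by -0.02 to +0.04. The real downside arises if the true curve is close to log-linear. The 5 mg estimate is then shrunk more (with a true effect of -1.46, means of -0.87 to -1.26 against -0.87 to -1.35 for the SAP contest), and its coverage can be several points lower. The log-linear sensitivity analysis would show that case.

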**7.1.3.5. Statistical Analyses / Methods**

**7.1.3.5.1. Bayesian MMRM Methodology Specification**

Endpoint / Variables

 
Change from baseline in monthly E-RS: COPD total and subscale scores
 

Model Specification

 
Bayesian mixed models repeated measures approach.
 
The model will include treatment*visit, baseline*visit, country and smoking status parameters. Note that the model will not include an intercept. Visit will consist of six levels (Month 1-Month 6), and Treatment will consist of six levels (placebo and 5 active doses). If the model does not run, the country covariate will be removed.
 
The priors for the mean vector for each of the parameters (i.e covariates) will each follow a normal distribution with mean 0 and SD 1000. The prior for the variance-covariance will follow an inverse Wishart distribution with degrees of freedom equal to the number of visits and an identity scale array. 150,000 samples will be generated with a thin of 75 after a burn-in of 10,000 samples. The number of samples or thin may be increased as needed to reduce the MCSE/SD<0.01 as deemed necessary.
 
Three chains will be used to calculate the gelman-rubin R statistic:             
 
Chain 1: The starting value for all covariates in the model will be 0.
 
Chain 2: The starting value for all covariates in the model will be 2.
 
Chain 3: The starting value for all covariates in the model will be -2.
 
 
 
The seeds used to for the three chains were generated using the ranuni function in SAS and are listed in Section 14.5.2.
 
All post-burn-in samples will be used when creating outputs.
 

Model Checking & Diagnostics

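### The primary dose-response fit is guaranteed only without covariates, and no candidate puts baseline and smoking status on E0 alone, so precision may be lost needlessly

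*SAP*

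**What the plan says.** SAP 7.1.1.5.1 lists log-linear, 3-parameter Emax and 4-parameter Emax curves, to be "fitted without adjusting for covariates. If possible, covariates (i.e., baseline, smoking status, country) will be included in the" E0 and Emax terms for the final analysis. It does not say what makes inclusion possible, or who decides. Selection then follows one rule: "The best fitting model will be the model with the smallest average DIC over the 3 chains where convergence is deemed to have been achieved". An adjusted model can therefore be the reported one: "If the best fitting model is one that adjusts for covariates, all outputs will be presented adjusting for the mean in the observed covariate".

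On the functional uniform prior (FUP), the same section says the "prior density for the FUP is based on all the parameters in the model" and that "the density will be calculated for values of dose from 0.0001 to 50 in steps of 5". It lists no covariate values to go with those doses. Starting values are given only for E0, Emax, ED50, m and the residual variance.

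Protocol 10.5.1.1 is firmer on smoking. Smoking status will be a covariate, with asymptotes allowed to differ by smoking status and at most six parameters. The nested simpler models include a fixed smoker/non-smoker difference (parallel curves) and no difference at all. Baseline and country are not mentioned for this model. Protocol 10.3 stratifies randomisation by smoking status.

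Elsewhere the SAP adjusts without such a condition. For the Bayesian longitudinal model (7.1.3.5.1), "The model will include treatment*visit, baseline*visit, country and smoking status parameters", and country is dropped if that model does not run. Smoking status is also an unconditional term in the frequentist MMRM, exacerbation-rate, time-to-event and responder models. SAP Table 1, which lists changes from the protocol, does not mention the handling of smoking status in the primary model.

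**The concern.** The primary objective is to characterise the dose response and choose doses. Baseline E-RS is collected in everyone randomised and is likely to be the strongest predictor of the change score. The plan nevertheless guarantees only a fit that ignores it, and the one adjusted alternative lets every covariate modify Emax as well as E0. The ordinary middle course, additive terms on E0 with a common Emax, is not listed.

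There is also a presentational risk. The primary figure shows the fitted curve "overlaid with the Month 6 adjusted posterior means and 90% CrI from the longitudinal model", and those means are adjusted for baseline, country and smoking status. If the curve is unadjusted, chance baseline imbalance would look like lack of fit.

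**Working it through.** **1. The plan's own figure.** Inputs: 90% two-sided intervals (protocol 10.5); SD 6.5 and the Table 4 effects (10.2); 600 randomised equally to six arms, so 100 per arm (5.2, 10.3); 10% dropout, so 540 completers, 90 per arm (5.2). Protocol 10.2 states that the interval for 35 mg minus placebo excludes 0 in over 80% of simulations in all three scenarios.

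- Pairwise comparison, 100 per arm: 85.9%, 56.7% and 70.2% (Scenarios 1, 2, 3). This does not give the stated figure.
- Unadjusted 4-parameter Emax with FUP, SD treated as known, 10,000 trials: 99.2%, 84.9% and 89.9% at 100 per arm; 98.5%, 82.1% and 86.6% at 90 per arm.

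The model-based figures agree with the protocol, and they need no covariates.

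**2. Size of the adjusted form.** Baseline 1 + smoking 1 + country 8 (nine countries, SAP 5.4.2) = 10 terms. In both E0 and Emax that is 20. The mean model then has 3 + 20 = 23 parameters (3-parameter Emax) or 4 + 20 = 24 (4-parameter), against at most six in the protocol. E0 only needs 2 extra terms, or 10 with country.

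**3. Gain from baseline on E0.** With equal variances s², the change score has variance 2s²(1 − r) and the adjusted residual has s²(1 − r²). The ratio is (1 + r)/2. Extra completers = 540 × (2/(1 + r) − 1).

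| r (assumed) | Variance ratio | Residual SD | Interval narrower by | Worth in completers |
|---|---|---|---|---|
| 0.5 | 0.75 | 5.63 | 13% | 180 |
| 0.6 | 0.80 | 5.81 | 11% | 135 |
| 0.7 | 0.85 | 5.99 | 8% | 95 |
| 0.8 | 0.90 | 6.17 | 5% | 60 |
| 0.9 | 0.95 | 6.33 | 3% | 28 |

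**4. Effect on success.** Scenario 2, 35 mg, 90 per arm, success = posterior probability above 95% that the difference is below 0. The level depends on how the FUP is coded, but the direction does not. Three codings of the 3-parameter curve give, for r = 0.5 and r = 0.8:

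- 79.6% to 89.8%, and 79.9% to 84.0%
- 77.3% to 86.3%, and 75.6% to 78.7%
- 90.1% to 95.1%, and 90.1% to 92.3%

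The gain is therefore about 2 to 10 points. The 4-parameter curve of step 1 moves from 82.1% to 89.9% (r = 0.5), 85.3% (r = 0.8) and 83.1% (r = 0.9).

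**5. How far the reported estimate could move.** For the Emax estimate at 35 mg (Scenario 2, 90 per arm, 3-parameter curve), the unadjusted and adjusted values differ with SD about 0.33 (r = 0.5) falling to about 0.2 (r = 0.8). They differ by more than 0.5 points in about 13% falling to about 2% of trials. The assumed effect is 1.667.

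**6. Which fit DIC would report.** With the FUP over all parameters, the 20-term form beat the unadjusted form in 99.5% to 100% of runs for r = 0.5 to 0.8 (400 runs per setting, smoking and country as noise). In large samples, k extra terms pay for themselves once the observed R² exceeds 1 − exp(−2k/540). That is 7.1% for k = 20, 3.6% for k = 10 and 0.4% for k = 1. At r = 0.9 baseline explains 5%, so 540 × ln(1/0.95) = 27.7 against a penalty of 40. Chance fit from the 19 useless terms adds roughly 19, so the net is about +7 and DIC could go either way. Baseline alone on E0 would gain 27.7 − 2 = 25.7.

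**7. If the 20-term form is reported.** FUP over all parameters, r = 0.6, true interactions zero, RMSE:

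| Setting | Unadjusted | 20-term | Additive |
|---|---|---|---|
| 3-parameter, Scenario 2, 35 mg | 0.76 | 0.66 | 0.65 |
| 3-parameter, Scenario 3, 25 mg | 0.59 | 0.63 | 0.53 |
| DIC-chosen shape, Scenario 2, 35 mg | 0.61 | 0.64 | 0.58 |
| DIC-chosen shape, Scenario 3, 25 mg | 0.76 | 0.85 | 0.70 |

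**The case against.** The best reply is that the unadjusted branch is unlikely. If the covariate model runs and converges, DIC nearly always picks it over the assumed range of r, and SAP 5.3 and 5.4.1 show a general intent to use these covariates. That stands, and it limits the expected loss. It does not remove it: DIC can choose only among models that were attempted and converged, and the SAP guarantees neither.

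Second, the Bayesian MMRM already reports adjusted Month 6 differences and the probabilities of falling below 0, −0.5, −1, −1.5 and −2 for each dose. This is a real mitigation for dose selection. But SAP 7.1.1.2 takes the primary summary measure from the dose-response model.

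Third, the size rests on assumptions. The documents give no r, and do not say whether 6.5 is a raw, change-score or adjusted SD. If r is 0.9, the gain is about 1 point.

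Two stronger readings are tempting but unsupported. A reader might infer that the 20-term form would flatten the curve to a line. That needs a FUP built as if there were one Emax, whereas the SAP bases the density on all parameters. What remains is narrower: the covariate values used with the dose grid, and the starting values for covariate terms, are not stated. A reader might also take the gap between unadjusted and adjusted categorical contrasts (SD 0.32 to 0.49) as the possible shift in the primary result. The primary analysis reports the Emax estimate, for which the gap is smaller (step 5).

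**Conclusion.** The point holds as an avoidable weakness of specification. The SAP makes only unadjusted primary fits definite, leaves the condition for adjustment undefined, and omits the additive form that the protocol names for smoking status.

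If the unadjusted fit is reported, residual variance is 11% to 33% larger than it need be for r = 0.8 to 0.5 (1/0.90 and 1/0.75), with the consequences in steps 3 to 5. These rest on equal variances, 6.5 as the change-score SD and the assumed r. If the 20-term form is reported instead, it is close to the additive form at 35 mg in Scenario 2 for a fixed 3-parameter curve, but less precise at 25 mg in Scenario 3.

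A reader might infer a protocol breach, bias, or an underpowered trial. The documents support none of these. The protocol allows a model with no smoking difference and never promised baseline adjustment. Leaving out baseline covariates does not bias a randomised comparison of change scores. The statement of over 80% at 600 participants reproduces without covariates.

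**What to change.** - Include centred baseline E-RS and smoking status as mandatory additive terms on E0, with a common Emax, in all three candidate curves. Choose the dose shape by DIC among these adjusted models.
- Add country to E0, and drop it first if the model does not run, as the Bayesian MMRM already does.
- Keep the protocol's smoking-specific-asymptote model as a pre-specified candidate or sensitivity analysis.
- State priors and starting values for the covariate terms. If any covariate acts on Emax, state the covariate values at which the FUP density is evaluated.
- Record the change in smoking handling and the added covariates in SAP Table 1.

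The cost is a few lines of text and code, and two extra linear parameters (ten with country) in place of about 20. It is nearly free: in simulation with country as pure noise, adding country to E0 changed 35 mg success by at most 0.6 points (84.0% to 83.4% at r = 0.8). No new data are needed.
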